8.8. Treatment of Overdose

For this study, any dose of GSK2831781 greater than the agreed dose level and frequency for a particular cohort will be considered an overdose.

GSK does not recommend specific treatment for an overdose.

In the event that an overdose is identified by unblinded staff, but is less than 450 mg in a 7 day period, this should be documented by the unblinded monitor (including the quantity and duration of the overdosing), but no additional action need be taken.

If the total dose administered has exceeded 450 mg in a 7 day period, the unblinded monitor should:

1. Contact the Medical Monitor immediately.
2. Ask the Medical Monitor to request that the Investigator closely monitors the participant for AE/SAE and laboratory abnormalities for at least 4 weeks from the date the overdose occurred, and thereafter as advised by the Medical Monitor.
3. If the overdose is identified within 21 days of its occurrence, request that the Medical Monitor advises the Investigator to obtain a plasma sample for PK analysis as soon as possible, and thereafter as advised by the Medical Monitor.
4. Document the quantity of the excess dose as well as the duration of the overdosing

9. STATISTICAL CONSIDERATIONS

9.1. Statistical Hypotheses

The first primary objective of this study is to assess the safety and tolerability of GSK2831781 in participants with moderate to severe UC. No formal hypotheses will be tested for this objective.

The second primary objective of this study is to evaluate the dose-response relationship in the change from baseline in the Complete 4-domain Mayo score, following 10 weeks of treatment with GSK2831781 or placebo. The dose response relationship will be characterised using the posterior probabilities of the parameters of an Emax model and by estimating the response at each dose level, using Bayesian methodologies, this will be the primary efficacy analysis. The primary efficacy analysis will therefore not use frequentist hypothesis testing, a characteristic of a well fitted model will be that the half width of the 95% credible interval for the change from baseline in Complete 4-domain Mayo response at ED90 is ≤ 1 . The dose-response relationship will also be assessed for selected categorical secondary endpoints (Endoscopic Improvement, Clinical Response and Clinical Remission).

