6.7. Dose Modification

Dose regimens (levels and/or frequencies) of GSK2831781 as described in Section 4.3 may be modified up or down based on ongoing review of the unblinded safety, pharmacokinetic, pharmacodynamic, biomarker and efficacy data by the DRC. However, exposure levels will not exceed those of the GSK2831781 450 mg dose regimen.

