9.2. Sample Size Determination

9.2.1. Sample Size Assumptions

Approximately 242 participants will be randomly assigned to study intervention under the assumption that a proportion will not be able to provide a Week 10 Complete 4-domain Mayo score assessment under the additional (hypothetical) estimand. If the attrition rate is higher than planned for (e.g., 15% or more) then additional participants, up to a maximum of 320, may be recruited.

Primary Analysis: Dose-response change from baseline in Mayo score

[figure not shown]
At Week 10 the expected distribution of the change from baseline in the continuous Mayo score in the placebo group is a mean of -1 and a standard deviation of 1.5 (based on tofacitinib Phase II data [[Sandborn](#), 2012]). Based on these assumptions the proposed sample size of 68 participants on the GSK2831781 450mg dose level, 42 participants on each of the GSK2831781 lower dose levels, and 48 participants on placebo are sufficient to characterise the dose-response curve. This is based on 5000 simulated trials where the following Emax model was fitted to simulated data:

$$Y = E0 + Emax * (Di)^\gamma / \{ED50^\gamma + (Di)^\gamma\}$$

Where E0 is the minimum dose effect, Emax is the maximum achievable effect above placebo, ED50 is the dose at half Emax, Di are doses = 0, 45, 150, 300, 450 and γ is the slope parameter (shape of the potential dose response curve). Y is the change from baseline in the continuous Mayo score. E0 is the assumed effect with Dose=0 (placebo) which is -1, the Emax is taken as -3, γ is assumed to be 1 and ED50 is assumed to be 100.

For the E0 and Emax parameters a normal prior with mean 0 and standard deviation of 100 was used. For ED50 a beta(0.5, 5.2) was used scaled between 0 and 675 (1.5*top dose, as suggested by [Bornkamp](#), 2014 as an approximation to the functional uniform prior). For the standard deviation a gamma (shape=2, rate=0.1) was used ([Chung](#), 2013).

[Figure 4](#) below illustrates a sample of fitted model curves. In these simulations the half width of the 95% credible interval for the Complete Mayo response at ED90 is ≤ 1 97% of the time:

Figure 4 Dose-response precision based on outlined assumptions

Note: True means from simulation marked in blue

To illustrate the properties of this sample size if it were to be analysed within a frequentist framework, the following sample size assessment is also provided:

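### The protocol's precision target for the dose-response model sits at ED90, which is 900 mg on the assumed curve, and its 97% makes no allowance for missing Week 10 scores

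*Protocol*

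**What the plan says.** Protocol Section 9.1 makes a Bayesian Emax model the primary efficacy analysis. It offers one numeric property of a good fit: that "the half width of the 95% credible interval for the change from baseline in Complete 4-domain Mayo response at ED90" is no more than 1.

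Section 9.2.1 justifies the sample size by simulating 5,000 trials. The placebo change has "a mean of -1 and a standard deviation of 1.5"; for the curve, "the Emax is taken as -3, γ is assumed to be 1 and ED50 is assumed to be 100"; and "Di are doses = 0, 45, 150, 300, 450". The arms are "68 participants on the GSK2831781 450mg dose level, 42 participants on each of the GSK2831781 lower dose levels, and 48 participants on placebo". The half-width criterion is reported as met in 97% of trials.

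The same section randomises about 242 and expects that some will not supply a Week 10 Complete Mayo score under the additional, hypothetical estimand. The Synopsis and Section 4.1.3 describe the expected loss as missed doses, an incomplete Week 10 score, or both. No planned rate is given. A rate of 15% or more is cited as an example of exceeding the plan, which would allow recruitment up to 320.

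**The concern.** There are two difficulties. First, neither section says which dose ED90 is. If it lies beyond 450 mg, the stated precision belongs to a part of the curve where no arm provides data. The analysis, however, sets out to estimate the response at each dose given, and no credible-interval target is stated for any of those doses. Calling the property a sign of good fit adds to this, because a wrong curve can have narrow intervals and a right one wide intervals.

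Second, if the simulated arms contain everyone randomised, the 97% belongs to a trial with no missing Week 10 scores, which the section does not expect.

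At stake is whether the quoted operating characteristic describes the trial that was designed.

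**Working it through.** **Inputs (Protocol 9.2.1 unless noted).** E0 = −1, Emax = −3, slope γ = 1, ED50 = 100 mg, SD = 1.5; doses 0, 45, 150, 300, 450 mg; arms 48, 42, 42, 42, 68 in that order. Priors: Normal(0, SD 100) for E0 and Emax; 675 × Beta(0.5, 5.2) for ED50; Gamma(2, 0.1) for the residual SD. First stage 40 on 450 mg and 20 on placebo; second stage 2:3:3:3:2 (Section 4.1).

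**1. Where ED90 lies.** Setting D^γ / (ED50^γ + D^γ) = 0.9 gives ED90 = ED50 × 9^(1/γ) = 100 × 9 = 900 mg, and 900/450 = 2.0 times the top dose. At 450 mg the curve reaches 450/550 = 81.8% of Emax. The assumed mean there is −1 − 3 × 0.818 = −3.45, against −1 − 0.9 × 3 = −3.70 at ED90.

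**2. What the 242 contains.** After the first 60, 242 − 60 = 182 remain. Over 2+3+3+3+2 = 13 units that is 14 per unit. So 450 mg has 40 + 28 = 68, placebo has 20 + 28 = 48, and each lower dose has 3 × 14 = 42. The total is 68 + 126 + 48 = 242. These are the randomised numbers with nothing taken off.

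**3. Reproducing the 97%.** The response at ED90 is E0 + 0.9 × Emax. Data were simulated from the assumed curve, and the three-parameter model (γ fixed at 1, since no prior for γ is given for the simulation) was fitted with the stated priors by grid integration. Repeated runs, mostly 2,000 to 3,000 trials per scenario, gave 96.7% to 97.9% with all 242 observed, so the plan's figure reproduces. Reading the target as the response at a fixed dose of 900 mg gives 100%, so the 97% matches the E0 + 0.9 × Emax reading.

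**4. Adding loss.** The rates are assumptions, applied equally to all arms with no extra recruitment.

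| Loss | Analysed | Half-width at ED90 ≤ 1 |
|---|---|---|
| 0% | 242 | 96.7–97.9% |
| 5% | about 230 | 96.0–96.6% |
| 10% | 218 | 94.8–96.3% |
| 15% | 207 | 92.6–94.8% |
| 20% | 194 | 91.7–93.0% |

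The percentage alone cannot separate no loss from roughly 10% loss. The inference that nobody was removed rests on the arm sizes in step 2.

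**5. Precision where the doses are.** Median half-widths of the 95% credible interval:

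| Quantity | 242 analysed | 15% loss |
|---|---|---|
| Response at ED90 | 0.70 | 0.75 |
| Response at 450 mg | 0.30 | 0.32 |
| 450 mg minus placebo | 0.50 | 0.54 |
| 45 mg minus placebo | 0.46 | 0.49 |

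At 450 mg the response half-width was below 1 in essentially every trial, so the threshold of 1 is decided by the extrapolation. Averaged over trials, the posterior puts 86% of its mass on ED90 above 450 mg.

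A hand check from arm means alone gives 1.96 × 1.5 × √(1/68 + 1/48) = 0.55 for 450 mg against placebo and 1.96 × 1.5 × √(1/42 + 1/48) = 0.62 for each lower dose. The model-based values are smaller because the curve pools the arms.

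**The case against.** The strongest defence is that ED90 is a conventional curve summary. E0 + 0.9 × Emax is a legitimate near-plateau quantity and does not imply that anyone receives 900 mg. It is also the harder target: 0.70 against 0.30 at 450 mg. Section 9.4.1 plans a 95% credible interval for each dose relative to placebo, and compares candidate models by DIC, so relative fit is handled elsewhere. Figure 4 is not in the text available here and may show precision across the range. The value of 900 mg also depends on slope 1. The primary model estimates the slope, and with ED50 at 100 mg, ED90 falls within 450 mg once γ exceeds ln 9 / ln 4.5 = 1.46. All of this stands. It limits the point but does not remove it, because the 97% was computed on the slope-1 curve and no target is stated for any studied dose.

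Several stronger readings are tempting but unsupported.

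- **That the criterion decides success.** Section 9.1 calls it one characteristic of a good fit. Decisions at Interim Analysis 3 and at primary completion rest on endoscopic healing.
- **That it breaches the exposure limit.** Section 6.7 says "exposure levels will not exceed those of the GSK2831781 450 mg dose regimen", but that governs dose changes by the Data Review Committee, not model summaries.
- **That the 97% flatters precision in the studied range.** The reverse is true, since ED90 is the stricter target.
- **That 97% should simply become 94%.** The 15% is an example of exceeding the plan, answered by further recruitment. The attrition sentence in Section 9.2.1 also concerns the hypothetical estimand, which discards scores after discontinuation, excluded medication, wrong dosing or unblinding. The primary treatment-policy estimand keeps scores after discontinuation except for COVID-19 reasons, so its loss may be smaller.

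**Conclusion.** The point holds in a limited form. On the plan's own assumptions, the only numeric precision target for the primary dose-response model applies at 900 mg, outside the doses studied, and it is described as fit when it measures precision. The 97% is correct for 242 complete participants but not for a trial with the losses the section expects: about 95–96% at 10% loss and 93–95% at 15%. The shortfall is therefore 1 to 4 points, depending on a rate the plan does not give.

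These figures assume slope 1, the stated priors, SD 1.5 and equal loss across arms. The four-parameter primary model was not simulated.

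The consequence is small. Precision in the studied range is comfortable and the sample size is not in doubt. After termination, SAP Section 2.1.4 confined the analysis of the Complete Mayo score to 450 mg and placebo, so the point bears on the protocol's design justification and not on the final analysis.

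**What to change.** In Sections 9.1 and 9.2.1:

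1. Describe the half-width as a precision target, not a sign of model fit.
2. State that ED90 is 900 mg under the assumed curve, so the figure there is an extrapolation.
3. Add the expected half-width of the 95% credible interval for the difference from placebo at each studied dose. With slope 1 it is about 0.5 at both 450 mg and 45 mg; the values at 150 and 300 mg should come from the same rerun.
4. Present the 97% as the value with no loss, and add a range by assumed attrition, for example 5%, 10% and 15%, naming the estimand to which each loss rate applies.

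The cost is wording and one rerun of the simulation, ideally repeated with the slope estimated, since that is the primary model. The sample size and design stay as they are.

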9.2. Sample Size Determination

9.2.1. Sample Size Assumptions

Approximately 242 participants will be randomly assigned to study intervention under the assumption that a proportion will not be able to provide a Week 10 Complete 4-domain Mayo score assessment under the additional (hypothetical) estimand. If the attrition rate is higher than planned for (e.g., 15% or more) then additional participants, up to a maximum of 320, may be recruited.

Primary Analysis: Dose-response change from baseline in Mayo score

[figure not shown]
At Week 10 the expected distribution of the change from baseline in the continuous Mayo score in the placebo group is a mean of -1 and a standard deviation of 1.5 (based on tofacitinib Phase II data [[Sandborn](#), 2012]). Based on these assumptions the proposed sample size of 68 participants on the GSK2831781 450mg dose level, 42 participants on each of the GSK2831781 lower dose levels, and 48 participants on placebo are sufficient to characterise the dose-response curve. This is based on 5000 simulated trials where the following Emax model was fitted to simulated data:

$$Y = E0 + Emax * (Di)^\gamma / \{ED50^\gamma + (Di)^\gamma\}$$

Where E0 is the minimum dose effect, Emax is the maximum achievable effect above placebo, ED50 is the dose at half Emax, Di are doses = 0, 45, 150, 300, 450 and γ is the slope parameter (shape of the potential dose response curve). Y is the change from baseline in the continuous Mayo score. E0 is the assumed effect with Dose=0 (placebo) which is -1, the Emax is taken as -3, γ is assumed to be 1 and ED50 is assumed to be 100.

For the E0 and Emax parameters a normal prior with mean 0 and standard deviation of 100 was used. For ED50 a beta(0.5, 5.2) was used scaled between 0 and 675 (1.5*top dose, as suggested by [Bornkamp](#), 2014 as an approximation to the functional uniform prior). For the standard deviation a gamma (shape=2, rate=0.1) was used ([Chung](#), 2013).

[Figure 4](#) below illustrates a sample of fitted model curves. In these simulations the half width of the 95% credible interval for the Complete Mayo response at ED90 is ≤ 1 97% of the time:

Figure 4 Dose-response precision based on outlined assumptions

Note: True means from simulation marked in blue

To illustrate the properties of this sample size if it were to be analysed within a frequentist framework, the following sample size assessment is also provided:

Assuming normal distributions with a standard deviation of 1.5, there would be greater than 90% power for a pairwise comparison to detect a difference from placebo of 2 points on the change from baseline at Week 10 in Complete 4-domain Mayo score between 42 participants randomised to GSK2831781 at one of the three lower dose levels and 48 participants randomised to placebo at a 5% significance level.

Interim Analysis 3 (See Section 9.5)

The sample size for the Interim Analysis 3 is based on the change from baseline in the Complete 4-domain Mayo score. With 40 participants randomised to GSK2831781 450 mg and 20 randomised to placebo, assuming a placebo change from baseline of -1 and standard deviation of 1.5, there would be 90% power to detect a clinically meaningful difference of 2 points on the Complete 4-domain Mayo score between GSK2831781 and placebo at a 5% significance level.

Decision rules at Interim Analysis 3 and at primary completion are based on the proportion of participants who achieve endoscopic healing. At Interim Analysis 3, the predictive probability of success at the end of the study will be also calculated based on the endoscopic healing data observed at this interim analysis and the sample size was also evaluated through the assessment of operating characteristics of decision rules based on

this endpoint. The study would be stopped for futility if the probability of success was low. With this number of participants, assuming a placebo response of 20%, if there was no effect of GSK2831781 then there would be a >80% probability that the study would stop at this point.

The Bayesian decision criteria including the definition of end-of-study success are outlined in the DRC charter. Supportive frequentist analyses for pairwise treatment differences in change from baseline in the Complete 4-domain Mayo score will be provided.

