9.4.1. Efficacy Analyses

Endpoint	Statistical Analysis Methods
Primary (efficacy)	
 Bayesian dose-response analyses will be conducted for change from baseline in the Complete 4-domain Mayo score at Week 10. The data will be initially analysed using an Emax model of the form: $Y = E0 + Emax * (Di)^\gamma / \{ ED50^\gamma + (Di)^\gamma \}$; where E0 is the minimum dose effect, Emax is the maximum achievable effect above placebo, ED50 is the dose at half Emax, Di are doses =0, 45, 150, 300, 450mg and γ is the slope parameter (shape of the potential sigmoid dose-response curve). Y is a measure of change from baseline in Mayo continuous score. Initially, normal vague priors will be used for E0, γ and Emax: Normal(0, sd=100). A functional uniform prior will be used for ED50 and h (Bornkamp, 2014), where the prior density for the functional uniform prior is based on all the parameters in the model. The parameterisation of the priors used in the analysis will be reported in the clinical study report. The primary dose-response model is the 4-parameter Emax model. Additional models will also be investigated: 3-parameter Emax model, power model, linear, quadratic, log-transformed dose. Each of the models will be fitted to the data and their fit compared using the Deviance Information Criterion (DIC). The model with the lowest DIC will be the primary model for inference if it shows a DIC difference from the 4-parameter Emax of at least 5. A four parameter Emax dose-response model, once fitted, will be used to estimate the minimally effective dose and 95% credible interval of each dose level relative to placebo.

Endpoint	Statistical Analysis Methods

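### The 97% precision figure behind the sample size holds for a beta(0.5, 5.2) prior on ED50 and does not carry over to the functional uniform prior that the beta is meant to approximate

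*Protocol*

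**What the plan says.** Protocol 9.2.1 calls the planned arms sufficient to characterise the dose-response curve: "68 participants on the GSK2831781 450mg dose level, 42 participants on each of the GSK2831781 lower dose levels, and 48 participants on placebo". The support is 5000 simulated trials with true E0 −1, Emax −3, ED50 100, slope 1 and SD 1.5. E0 and Emax have Normal(0, SD 100) priors and the SD has a gamma prior. On the remaining parameter the text reads: "For ED50 a beta(0.5, 5.2) was used scaled between 0 and 675", which it introduces "as an approximation to the functional uniform prior". No prior for the slope is listed. The result concerns one property: "In these simulations the half width of the 95% credible interval for the Complete Mayo response at ED90" is at most 1 in 97% of trials.

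Protocol 9.1 gives that property its role: "a characteristic of a well fitted model will be that the half width of the 95% credible interval" at ED90 is no more than 1.

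Protocol 9.4.1 makes the 4-parameter Emax model primary and states: "A functional uniform prior will be used for ED50 and h". It adds that "the prior density for the functional uniform prior is based on all the parameters in the model". It gives no bounds for ED50 or h. The symbol h is not defined there and is read here as the slope, although the same section also lists a Normal(0, SD 100) prior for the slope.

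**The concern.** The 97% is the only precision figure the protocol gives for its primary dose-response analysis, and it was obtained with a stand-in prior. That would be harmless if the stand-in behaved like the functional uniform prior for the property quoted. There is reason to doubt it. Under the assumed truth, ED90 solves d/(d + 100) = 0.9, so d = 900 mg, twice the top dose. The response there depends on how far the curve is extrapolated, and so on how much weight the posterior leaves on large ED50. With these arm sizes the data say little about that upper end, and the prior tail largely sets the interval width. A prior with a light upper tail will produce narrow intervals partly by construction.

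If so, a reader of 9.2.1 expects the protocol's own mark of a well fitted model to be missed in about 3 trials of 100, when the prior being approximated would miss it far more often.

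**Working it through.** **Inputs (Protocol 9.2.1).** "Di are doses = 0, 45, 150, 300, 450" mg; n = 48, 42, 42, 42, 68 (sum 48 + 3×42 + 68 = 242, so no attrition); E0 = −1, Emax = −3, ED50 = 100, slope 1, SD 1.5.

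**Model and target.** With θ for ED50, the mean at dose d is E0 + Emax·f, with f = d/(d + θ). The response at ED90 is E0 + 0.9·Emax. The half-width is (97.5% quantile − 2.5% quantile)/2.

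**Method.** For a given θ the model is linear in E0 and Emax, so their posterior is available in closed form. θ is handled on a grid up to 675 mg, and the interval is read from the resulting mixture. Each setting used several hundred to 5000 simulated trials, so the Monte Carlo error is at most about 2 percentage points.

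**Step 1: the plan's own figure.** The beta(0.5, 5.2) prior gives 97.3% and 97.1% in two runs of 5000 trials, so the stated 97% is reproduced. Reading the target as the response at 900 mg, or as 90% of the effect at 450 mg, gives 100%, so E0 + 0.9·Emax is the reading that fits.

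**Step 2: functional uniform priors at slope 1.**

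- ED50-only form: density proportional to the square root of the integral of (∂f/∂θ)² over 0–450 mg. Since ∂f/∂θ = −d/(d + θ)², the integral is 450³/(3θ(θ + 450)³), and the density is proportional to θ^(−1/2)·(θ + 450)^(−3/2). Truncated at 675, its distribution function is √(θ/(θ + 450)) / √(675/1125). Hence P(ED50 > 300) = 1 − √(0.4/0.6) = 18.4% (18.7% if the grid starts at 0.1 mg).
- Joint form: square root of the determinant of the Gram matrix of (1, f, ∂f/∂θ), taken over the five doses or over the continuous range, with or without the factor |Emax|.

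**Step 3: results, everything else as in 9.2.1.**

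| Prior on ED50 | P(ED50 > 300 mg) | P(half-width ≤ 1) | 90th percentile of half-width |
|---|---|---|---|
| Beta(0.5, 5.2) on 0–675 | 1.6% | 97% | 0.91–0.92 |
| Joint, without \|Emax\| (five doses or continuous range) | about 4–7% | about 66–73% | about 1.3 |
| Joint, with \|Emax\| | as above | about 59–65% | about 1.4 |
| ED50-only | about 18–19% | about 46–50% | about 1.5 |

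A separate Gibbs sampler with the exact gamma prior on the SD, run on 60 trials, gave 58/60 = 97% under the beta and 23/60 = 38% under the ED50-only form (standard error about 6 points). Its sample is small, but the contrast is the same.

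**Step 4: what this does not include.** The 675 mg bound is borrowed from 9.2.1. With a bound of 4500 mg the functional uniform figures fall to about 40–68%. Estimating the slope lowers them much further: with a functional uniform prior on ED50 and slope, ED50 up to 675 mg and assumed slope bounds of 0.5–5 or 0.5–10, the figure is about 6%. Keeping the beta on ED50 and adding a flat slope prior on 0.5–10 gives 57%. The slope bounds are assumptions, so these last figures show direction and are not values for the protocol to print.

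**The case against.** Several points on the other side are sound. The beta prior is stated openly and called an approximation, and the 97% is correct for the simulation described. A reader might infer an arithmetic error or a concealed change of prior; the text supports neither.

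A reader might also take about 46–73% as the chance that the planned analysis meets its criterion, and conclude that it would fail in 3 to 5 trials of 10. That does not follow. A slope-1 fit with a functional uniform prior on ED50 alone is not the 9.4.1 analysis, which estimates the slope. Section 9.4.1 also gives no bounds and leaves the parameterisation to the study report, so the documents fix no single figure.

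The practical reach is limited too. The loss of precision comes from extrapolating to 900 mg. For 90% of the effect reached at 450 mg, the half-width is at most 1 in 100% of simulated trials under every prior tried (median about 0.27–0.28). Section 9.1 presents the criterion as a feature of good fit, not a success rule. Section 9.2.1 adds more than 90% pairwise power, and bases the decisions at Interim Analysis 3 and primary completion on endoscopic healing. After termination the SAP (2.1.4, 2.4, 8.1.1.2) confines the primary model to 450 mg against placebo, with no ED50.

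All of this narrows the consequence. None of it carries the 97% from the beta to the prior it stands in for; pairwise power in particular says nothing about precision at ED90.

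**Conclusion.** The point holds for the protocol's sample-size justification. The 97% depends on the light upper tail of the beta(0.5, 5.2) prior. Replacing only that prior by a functional uniform one takes the figure to about 60–73% (joint form) or about 46–50% (ED50-only form), and the 90th percentile of the half-width from 0.91 to about 1.3–1.5. The assumptions are slope 1, ED50 truncated at 675 mg, response at ED90 = E0 + 0.9·Emax, and all 242 participants complete.

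No form of the functional uniform prior that was tried comes near 97%, so the conclusion does not depend on which form was intended. The size for the actual 9.4.1 analysis cannot be stated from the documents; estimating the slope and widening the bounds both lower it. No analysis reported under the SAP is affected.

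**What to change.** Any one of three changes would do:

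- In 9.2.1, re-run the simulation with the model and priors of 9.4.1 (slope estimated, functional uniform prior in the intended form, bounds on ED50 and slope stated) and replace the 97% with the result.
- Keep the 97% and label it as conditional on slope 1 and the beta(0.5, 5.2) prior, which 9.4.1 does not specify.
- If the beta is what the analysis was meant to use, name it as the ED50 prior in 9.4.1, and still say in 9.2.1 that the figure assumes slope 1.

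The slope-1 figures above should not be printed as the replacement, because they describe neither section's analysis. The cost is one re-run of existing code or one sentence of text, and probably a less favourable number. Participant numbers do not change.
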